10.11 MDA

Minimal Disease Activity is a state of disease activity deemed a useful derived target of treatment by both the patient and physician, given current treatment possibilities and limitations. Criteria shown in Table 10–3 covering all of the domains of the disease have been developed to determine whether or not a patient has reached MDA based on key outcome measures in PsA.

A subject is considered as having MDA if 5 or more of the following 7 criteria in [Table 10–3](#) are fulfilled:

Table 10–3: MDA criteria in PsA

A subject is classified as in MDA when they meet 5 of 7 of the following criteria:	

 • Tender joint count ≤ 1 • Swollen joint count ≤ 1 • PASI ≤ 1 or BSA ≤ 3 • Patient pain VAS ≤ 15 	
 • Patient global activity VAS ≤ 20 • HAQ ≤ 0.5 • Tender enthesial points ≤ 1

BSA=body surface area; HAQ=Health Assessment Questionnaire; MDA=minimal disease activity; PASI=Psoriasis Area and Severity Index; VAS=visual analog scale
Data sources: Mease, 2011; Coates et al, 2010

In addition, a modified MDA will be determined using the criteria in [Table 10–3](#) by fulfilling the criterion PASI ≤ 1 or BSA ≤ 3 and 4 out of the 6 remaining criteria.

10.12 DAS28(CRP)

The components for DAS28(CRP) include the TJC and SJC based on 28 joints ([Section 10.2](#)), CRP ([Section 10.7](#)) and the PGADA ([Section 10.3](#)). DAS28(CRP) is calculated as follows:

$$DAS28(CRP) = 0.56 \cdot \sqrt{TJC} + 0.28 \cdot \sqrt{SJC} + 0.014 \cdot PGADA + 0.36 \cdot \ln(CRP + 1) + 0.96$$

10.13 MASES

The MASES is an index that measures the severity (ie, intensity and extent) of enthesitis through the assessment of 13 entheses (bilateral costochondral 1, costochondral 7, anterior superior iliac spine, posterior iliac spine, iliac crest and proximal insertion of the Achilles tendon sites, and the fifth lumbar vertebral body spinous process) (Heuft-Dorenbosch et al, 2003) each scored as 0 or 1 and then summed for a possible score of 0 to 13.

10.14 LDI

Dactylitis, the swelling of an entire digit related to articular and peri-articular inflammation, is a characteristic of inflammatory spondyloarthropathies, including PsA. Presence of dactylitis will be assessed using the LDI basic which evaluates for a $\geq 10\%$ difference in the circumference of the digit compared to the opposite digit (Healy and Helliwell, 2007; Helliwell et al, 2005). This is then multiplied by the tenderness score, using a simple grading system (0=absent, 1=present). The digits involved and the matching contralateral digit will also be recorded at the same visits.

10.15 Hospital Anxiety and Depression Scale

The HADS was chosen for its well-established psychometric properties and its use in clinical research on biological therapy in subjects with chronic plaque PSO (Langley et al, 2010; Dauden et al, 2009). The HADS scores for anxiety and for depression range from 0 to 21 with higher scores indicating worse state. A score below 8 is considered to be normal whereas a score of 15 and above is considered severe (Snaith and Zigmond, 1994).

10.16 PsAID-9

The PsAID-9 is a patient-reported outcome measure for assessing the impact of PsA in 9 physical and psychological domains, including pain, fatigue, skin problems, work and/or leisure activities, functional capacity, discomfort, sleep disturbance, coping, and anxiety/fear/uncertainty. Each domain is assessed with a single question using a 0 to 10 numerical rating scale. Each domain score is multiplied by a weighting factor and the results are then summed to provide the total score. The total score ranges from 0 to 10, with higher scores indicating a worse status. The PsAID-9 demonstrated satisfactory psychometric properties in an international validation study; however, further validation is needed (Gossec et al, 2014). A score below 4 out of 10 is considered a patient-acceptable status. A change of 3 or more points is considered relevant absolute change.

10.17 SF-36

The SF-36 (Version 2, standard recall) is a 36-item generic Health-Related Quality of Life (HRQoL) instrument that uses a recall period of 4 weeks. Items are grouped into 8 domains as follows: Physical Functioning (10 items), Role Physical (4 items), Bodily Pain (2 items), General Health (5 items), Vitality (4 items), Social Functioning (2 items), Role Emotional (3 items), Mental Health (5 items), and 1 item for perceived stability or change in health (Health Transition) during the last year. The concepts represented by these domains contribute to physical, mental, and social aspects of HRQoL.

In addition to domain scores, the Physical Component Summary and Mental Component Summary scores are calculated from the 8 domains (excluding the Health Transition item). Component scores appreciate the impact of each domain on physical and mental health status (Maruish, 2011). Each of the 8 domain scores and the component summary scores range from 0 to 100, with a higher score indicating a better health status. The 2 component summary scores are standardized with a mean of 50 and a standard deviation of 10 in the general US population.

11 ASSESSMENT OF IMMUNOGENICITY

The Investigator or designee will obtain blood samples for measurement of bimekizumab plasma concentrations and antibodies to bimekizumab at the time points specified in [Table 5–1](#). When these samples are required at a visit during which the subject is dosed with IMP, the blood samples will be drawn prior to dosing. Samples should be drawn at the same time of the sampling for clinical laboratory tests. The time and date of collection will be recorded in the eCRF. Instructions pertaining to sample collection, processing, storage, labeling, and shipping are provided in the laboratory manual for this study. Any characterization of the anti-bimekizumab antibody response will be done using validated assays. Detailed information on sample analysis will be provided in a bioanalytical report.

12 STUDY MANAGEMENT AND ADMINISTRATION

12.1 Adherence to protocol

The investigator should not deviate from the protocol. However, the investigator should take any measure necessary in deviation from or not defined by the protocol in order to protect clinical study subjects from any immediate hazard to their health and safety. In this case, this action

should be taken immediately, without prior notification of the regulatory authority, IRB/IEC, or sponsor.

After implementation of such measure, the investigator must notify the Clinical Project Manager of the sponsor within 24 hours and follow any local regulatory requirements.

12.2 Monitoring

UCB (or designee) will monitor the study to meet the sponsor's monitoring Standard Operating Procedures (SOPs), ICH-GCP guideline, and applicable regulatory requirements, and to ensure that study initiation, conduct, and closure are adequate. Monitoring of the study may be delegated by UCB to a CRO or a contract monitor.

The investigator and his/her staff are expected to cooperate with UCB (or designee) and to be available during the monitoring visits to answer questions sufficiently and to provide any missing information. The investigator(s)/institution(s) will permit direct access to source data/documents for study-related monitoring, audits, IRB/IEC review, and regulatory inspection(s).

The investigator will allow UCB (or designee) to periodically review all eCRFs and corresponding source documents (eg, hospital and laboratory records for each study participant). Monitoring visits will provide UCB (or designee) with the opportunity to evaluate the progress of the study, verify the accuracy and completeness of eCRFs, ensure that all protocol requirements, applicable authorities' regulations, and investigator's obligations are being fulfilled, and resolve any inconsistencies in the study records.

12.2.1 Definition of source data

All source documents must be accurate, clear, unambiguous, permanent, and capable of being audited. They should be made using some permanent form of recording (ink, typing, printing, optical disc). They should not be obscured by correction fluid or have temporary attachments (such as removable self-stick notes). Photocopies and/or printouts of eCRFs are not considered acceptable source documents.

Source documents are original records in which raw data are first recorded. These may include hospital/clinic/general practitioner records, charts, diaries, x-rays, laboratory results, printouts, pharmacy records, care records, ECG or other printouts, completed scales, or quality of life questionnaires, for example. Source documents should be kept in a secure, limited access area.

Sponsor or designee will review to ensure that computerized source documents produced by the site are compliant with Food and Drug Administration (FDA) Part 11 requirements and document appropriately. Source documents that are computer generated and stored electronically must be printed for review by the monitor (eg, ECG reports). Once printed, these copies should be signed and dated by the Investigator and become a permanent part of the subject's source documents. The Investigator will facilitate the process for enabling the monitor to compare the content of the printout and the data stored in the computer to ensure all data are consistent.

Electronic data records must be saved and stored as instructed by UCB (or designee).

12.2.2 Source data verification

Source data verification ensures accuracy and credibility of the data obtained. During monitoring visits, reported data are reviewed with regard to being accurate, complete, and verifiable from

source documents (eg, subject files, recordings from automated instruments, tracings [ECG], x-ray films, laboratory notes). All data reported on the eCRF should be supported by source documents, unless otherwise specified in [Section 12.2.1](#).

12.3 Data handling

12.3.1 Case Report form completion

This study will use electronic data capture (EDC); the Investigator is responsible for prompt reporting of accurate, complete, and legible data in the eCRF and in all required reports.

This study will also use an electronic device (Site Tablet) to capture patient reported outcomes.

Serious AE reporting will be done using the SAE Report Form (see [Section 9.2.2](#)) while also entering the event in the appropriate eCRF section. The safety database and the clinical database will be reconciled during the study and discrepancies will be corrected as needed.

The Investigator should maintain a list of personnel authorized to enter data into the eCRF. Access to the EDC will be given after training has been received. A training certificate will be provided and filed.

Detailed instructions on the use of the EDC will be provided in the eCRF Completion Guidelines.

Corrections made after the Investigator's review and approval (by means of a password/electronic signature) will be re-approved by the Investigator. Any change or correction to the eCRF after saving must be accompanied by a reason for the change.

12.3.2 Database entry and reconciliation

Case Report forms/external electronic data will be entered/loaded into a validated electronic database using a clinical data management system (CDMS). Computerized data cleaning checks will be used in addition to manual review to check for discrepancies and to ensure consistency of the data. This study is performed using EDC: the data are entered into the eCRFs once and are subsequently verified.

An electronic audit trail system will be maintained within the CDMS to track all data changes in the database once the data have been saved initially into the system or electronically loaded. Regular backups of the electronic data will be performed.

12.3.3 Subject Screening and Enrollment log/Subject Identification Code list

The subject's screening and enrollment will be recorded in the Subject Screening and Enrollment Log.

The investigator will keep a Subject Identification Code list. This list remains with the investigator and is used for unambiguous identification of each subject.

The subject's consent and enrollment in the study must be recorded in the subject's medical record. These data should identify the study and document the dates of the subject's participation.

12.4 Termination of the study

UCB reserves the right to temporarily suspend or prematurely discontinue this study either at a single site, multiple sites, or at all sites at any time for reasons including, but not limited to, safety or ethical issues, inaccurate or incomplete data recording, noncompliance, or unsatisfactory enrollment with respect to quality or quantity.

If the study is prematurely terminated or suspended, UCB (or its representative) will inform the investigators/institutions and the regulatory authority(ies) of the termination or suspension and the reason(s) for the termination or suspension, in accordance with applicable regulatory requirement(s). The IRB/IEC should also be informed and provided with reason(s) for the termination or suspension by the sponsor or by the investigator/institution, as specified by the applicable regulatory requirement(s). In addition, arrangements will be made for the return of all unused IMP and other material in accordance with UCB procedures for the study.

12.5 Archiving and data retention

The investigator will maintain adequate records for the study, including eCRFs, medical records, laboratory results, Informed Consent documents, drug dispensing and disposition records, safety reports, information regarding participants who discontinued, and other pertinent data.

All essential documents are to be retained by the investigator until at least 2 years after the last approval of a marketing application in an ICH region and until there are no pending or contemplated marketing applications in an ICH region, or at least 2 years have elapsed since the formal discontinuation of clinical development of the IMP. These documents should be retained for a longer period, however, if required by the applicable regulatory requirement(s) or by an agreement with UCB (CPMP/ICH/135/95, 2002 [Section 4.9.5]). The investigator will contact UCB for authorization prior to the destruction of any study records or in the event of accidental loss or destruction of any study records. The investigator will also notify UCB should he/she relocate or move the study-related files to a location other than that specified in the sponsor's trial master file.

12.6 Audit and inspection

The investigator will permit study-related audits mandated by UCB, after reasonable notice, and inspections by domestic or foreign regulatory authorities.

The main purposes of an audit or inspection are to confirm that the rights and well-being of the subjects enrolled have been protected, that enrolled subjects (ie, signing consent and undergoing study procedures) are appropriate for the study, and that all data relevant for the evaluation of the IMP have been processed and reported in compliance with the planned arrangements, the protocol, investigational site, and IRB/IEC SOPs, ICH GCP, and applicable regulatory requirements.

The investigator will provide direct access to all study documents, source records, and source data. If an inspection by a regulatory authority is announced, the investigator will immediately inform UCB (or designee).

12.7 Good Clinical Practice

Noncompliance with the protocol, ICH-GCP, or local regulatory requirements by the investigator, institution, institution staff, or designees of the sponsor will lead to prompt action by UCB to secure compliance. Continued noncompliance may result in the termination of the site's involvement in the study.

13 STATISTICS

A description of statistical methods follows and will be described in more detail in the Statistical Analysis Plan.

13.1 Definition of analysis sets

The Enrolled Set (ES) will consist of all subjects who have given informed consent for PA0009.

The Safety Set (SS) will consist of all subjects who receive at least 1 dose of the IMP in PA0009.

The Full Analysis Set (FAS) will consist of all enrolled subjects who receive at least 1 dose of the IMP and have a valid measurement for at least 1 efficacy variable after PA0009 entry visit.

13.2 General statistical considerations

Summary statistics will consist of frequency tables for categorical variables. For continuous variables, summary statistics will consist of number of available observations, arithmetic mean, standard deviation, median, minimum, and maximum unless stated otherwise.

In general, summary statistics will be done by randomized treatment group and by treatment group at completion of PA0008 (ie, bimekizumab 160mg Q4W or bimekizumab 320mg Q4W).

Two subpopulations will be defined for this study. Subpopulation 1 will consist of all subjects who do not receive rescue therapy according to the criteria outlined in [Section 5.1.1](#).

Subpopulation 2 will consist of all subjects who receive rescue therapy according to the criteria outlined in [Section 5.1.1](#). Analyses of the primary and secondary variables will also be done on both subpopulations.

Changes from Baseline will be calculated relative to the Baseline of PA0008. Variables measured at the start of PA0009 will be referred to as PA0009 entry values.

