4.2.2 Secondary efficacy variables

The secondary efficacy variables are:

- ACR20, ACR50, and ACR70 response at Week 48
- Change from Baseline of PA0008 in MASES at Week 48
- Change from Baseline of PA0008 in the LDI at Week 48
- PASI75 and PASI90 response at Week 48

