7.8.1 Permitted concomitant treatments (medications and therapies)

Medication changes are permitted at any time after enrollment into this extension study. Medication changes and additions are permitted with the following guidelines:

- Nonsteroidal anti-inflammatory drugs (NSAIDs), DMARDs (methotrexate, sulfasalazine, leflunomide, apremilast), and/or joint injections may be given if deemed appropriate by the Investigator as outlined below. Subjects may receive these add-on therapies while continuing to receive bimekizumab. Under no circumstances should subjects have a concomitant biologic agent while receiving bimekizumab.
 - For subjects taking NSAIDs/cyclooxygenase-2 (COX-2) inhibitors, a change can be made to a different NSAID/COX-2. Changes from an NSAID to a COX-2 inhibitor or from a COX-2 inhibitor to an NSAID are permitted up to the maximum approved or

tolerated dose, whichever is less. Only 1 NSAID/COX-2 inhibitor may be taken at a given time.

- For subjects not taking NSAID/COX-2 inhibitors, either can be initiated, up to the maximum approved or tolerated dose, whichever is lower. Only 1 NSAID/COX-2 may be taken at a given time.
- Methotrexate may be added or increased to a maximum dose of 25mg/week, or the maximum tolerated dose, whichever is lower. The route of administration may be changed from oral to sc or from sc to oral. It is strongly recommended that subjects taking MTX should also take folic acid supplementation.
- Sulfasalazine may be given up to a maximum dose of 3g/day, or the maximum tolerated dose, whichever is lower, for peripheral arthritis symptoms.
- Leflunomide may be given at a maximum dose of 20mg/day (or an average of 20mg/day if not dosed daily), or the maximum tolerated dose, whichever is lower, for peripheral arthritis symptoms. Leflunomide should not be used concomitantly with MTX.
- Apremilast may be given at a maximum dose of 30mg twice daily, or the maximum tolerated dose, whichever is lower.
- Combination DMARDs (optimally 2) are allowed except that leflunomide and MTX may not be given together.
- No other oral DMARDs are permitted during this OLE study.
- Steroid tapers for disease activity or disease-related reasons are allowed with an average daily dose of 20mg prednisone or prednisone equivalent per day for a maximum of 14 days.

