#### **3.6.2 Safety Set**

The Safety Set (SS) will consist of all subjects in the ES who received at least one dose of study medication in PA0009.

All safety variables will be summarized for the SS. Pharmacokinetic and immunological variables will also be summarized on the SS.

Two Sub-populations of the SS will be defined for this study: SS Sub-population 1 will consist of all subjects in the SS who took no concomitant rescue medication in PA0009, and SS Sub-population 2 will consist of all subjects in the SS who took concomitant rescue medication in PA0009, as outlined in [Section 6.5](#). Rescue medications will be identified in the study database using the flag collected in the electronic case report form (eCRF). Concomitant medications are defined in [Section 6.4](#).

Selected summaries of the primary and secondary safety variables will be repeated for both SS Sub-populations only in the event that the number of subjects receiving rescue medication is  $\geq 10\%$  of the total number of subjects in the SS.

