#### **3.6.3 Full Analysis Set**

The Full Analysis Set (FAS) will consist of all subjects in the ES who received at least 1 dose of study medication in PA0009 and have a valid measurement for at least 1 efficacy variable after PA0009 EV.

Secondary and other efficacy variables will be summarized for the FAS. Immunological variables will also be summarized on the FAS where specified in [Section 9.2](#).

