### 3.10 Changes to protocol-defined analyses

The following changes have been made to the protocol-defined analyses:

- Summaries of ACR20, ACR50, ACR70, PASI75, PASI90, and PASI100 response at each post-PA0008 Baseline visit have been added for subjects who were responders at PA0008 Week 12. These summaries include all post-Baseline PA0008 visits through to PA0009 Week 104 and will be used to assess maintenance of response.
- Summaries of BSA at each visit in PA0009 have been added as an additional method of assessing response in order to provide information at visits where the PASI data may be missing.
- Summaries by randomized treatment in PA0008 will not be produced, as subjects will have been on a constant dose of bimekizumab 160mg or 320mg for at least 36 weeks prior to PA0009 entry. Maintenance of response displays will be split by treatment sequence across PA0008 and PA0009. Safety displays using PA0008 information will incorporate exposure in PA0008.
- The protocol stated that all safety analyses would be performed for both SS Sub-populations; instead only key safety analyses will be repeated by SS Sub-population as identified in [Section 10](#). These analyses will be performed only in the event that the number of subjects receiving rescue medication is  $\geq 10\%$  of the total number of subjects in the SS.
- The protocol stated that figures presenting the relationship between ACR20 response and ADAb positivity over time would be produced. This has been changed to use the ACR50 response instead as this is considered to be the key efficacy endpoint with respect to ACR.

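### The SAP drops the protocol's secondary efficacy summaries by rescue status without declaring it, and no planned efficacy table links Week 48 response to add-on therapy

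*Protocol*

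**What the plan says.** **Protocol.** Section 13.2 defines Subpopulation 1 (no rescue therapy) and Subpopulation 2 (rescue therapy) and then commits: "Analyses of the primary and secondary variables will also be done on both subpopulations". Section 4.2 holds both the secondary safety variable (4.2.1) and the secondary efficacy variables (4.2.2). The latter begin with "ACR20, ACR50, and ACR70 response at Week 48" and continue with MASES, LDI, PASI75 and PASI90 at Week 48.

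Section 7.8.1 allows treatment to be added freely: "Medication changes are permitted at any time after enrollment into this extension study". It names NSAIDs, methotrexate, sulfasalazine, leflunomide, apremilast and joint injections, and says "Subjects may receive these add-on therapies while continuing to receive bimekizumab". On systemic steroids: "Steroid tapers for disease activity or disease-related reasons are allowed", within limits.

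**SAP.** Section 3.6.2 defines the sub-populations within the Safety Set only: "Selected summaries of the primary and secondary safety variables will be repeated for both SS Sub-populations", and then only if at least 10% of that set receive rescue medication. Section 3.6.3 says "Secondary and other efficacy variables will be summarized for the FAS", with no rescue split. Section 3.10 records one change on this subject, and it concerns safety: "The protocol stated that all safety analyses would be performed for both SS Sub-populations", now reduced to key safety analyses. The amendment log (13.1.2) likewise speaks only of safety variables.

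**The concern.** The secondary objective is the long-term efficacy of bimekizumab. In a single-arm extension where background therapy can be intensified at any time, a Week 48 response rate describes bimekizumab plus whatever was added. The protocol foresaw this and promised the secondary variables by rescue status. The SAP omits that analysis for efficacy, and a reader of its list of changes would not learn of the omission. At stake are the completeness of the declared changes and whether the report can show how many Week 48 responders had started add-on therapy.

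**Working it through.** **1. Does the protocol commitment cover efficacy?** Section 13.2 says primary and secondary variables, and 4.2.2 places ACR, MASES, LDI and PASI among the secondary ones. A safety-only reading fits poorly, because 13.3.1 separately commits all safety analyses to both subpopulations.

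**2. What does the SAP keep?**

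| Place | Content on rescue status |
|---|---|
| SAP 3.6.2 | Safety Set sub-populations, safety variables only |
| SAP 3.6.3 | Full Analysis Set (FAS), no split |
| SAP 4.6 | Efficacy subset: not applicable |
| SAP 4.8, 8.4 | Subgroups: region, prior TNF inhibitor, disease duration, DMARD status at the start of PA0008; none uses therapy added in PA0009 |
| SAP 8.2, 8.3, 8.3.1 | No efficacy summary by rescue status |
| SAP 3.10, 13.1.2 | Safety reduction declared; efficacy omission not mentioned |

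The 10% trigger is 0.10 × 200 = 20 subjects at maximum enrolment. With 19 or fewer rescued there are no sub-population tables even for safety. For efficacy there are none at any level of use.

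**3. Does any imputation rule react to rescue?** Under SAP 4.2.1, missing data or dropout leads to nonresponder imputation (NRI); rescue does not. Under 13.1.2, efficacy data after prohibited medication are kept.

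**4. Partial safeguards.**
- SAP 8.1.1 scores an injected joint as tender and swollen for up to 364 days after the visit at which it was recorded. Week 48 is 48 × 7 = 336 days after first dose, or 343 with the 7-day window. A joint recorded as injected at any PA0009 visit up to Week 48 is therefore still counted as tender and swollen at Week 48. Both joint counts are required for ACR, so the rule matters there. It does not reach the other five ACR components, MASES, LDI or PASI, or any added DMARD, NSAID or systemic steroid.
- SAP 6.5 tabulates rescue use by category and lists it with start dates, but does not cross it with response.

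**5. Size.** The plan gives no figure to reproduce. Let *r* be the share with rescue started by Week 48, *q* the NRI response rate among them, and *p* the rate among the rest.

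- Planned rate = (1 − r)p + rq
- Rate with rescued subjects as nonresponders = (1 − r)p
- Gap = rq, which cannot exceed r

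Neither *r* nor *q* is in the documents. Assuming r = 10-25% and q = 40-60%:

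- Low: 0.10 × 0.40 = 4 points (8 of 200 subjects)
- High: 0.25 × 0.60 = 15 points (30 of 200 subjects)

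Over a wider assumed range, 0.05 × 0.30 = 1.5 points to 0.30 × 0.80 = 24 points.

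**The case against.** The study is a descriptive, single-arm safety extension with no efficacy hypothesis and no formal sample size. Protocol 13.4 specifies efficacy for all subjects in the FAS, and 13.4.1 lists no rescue subgroup, so a safety-focused reading by the SAP authors is understandable. Rescue is a post-entry event that depends on response, so the promised split could not isolate the drug effect anyway. SAP 13.1.2 also makes a reasoned choice to keep efficacy data after prohibited medication, because the primary purpose is safety.

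Much of this stands. It limits the consequence and shows that the promised split is descriptive. It does not cancel the general commitment in Protocol 13.2 or explain why SAP 3.10, which records a change as small as replacing ACR20 by ACR50 in an antibody figure, is silent here.

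A reader might infer that nothing in the plan addresses add-on therapy, or that responses after a joint injection count in full. The documents do not support either: injected joints are scored adversely through Week 48, and the extent of rescue use will be reported. In addition, Protocol 7.8.1 says that subjects with persistent active disease despite add-ons should be withdrawn at the investigator's discretion, and dropouts become nonresponders.

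**Conclusion.** The omission and the lack of declaration are confirmed by the text. The practical gap is that no planned efficacy table shows how much of the Week 48 response occurs on added DMARDs, NSAIDs or systemic steroids. The change should be made, but it does not affect the primary safety objective or invalidate the planned main analysis.

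The 4-15 points rest wholly on assumed rates. A reader might take them as the amount by which bimekizumab efficacy is overstated. They are not: they are the share of subjects who respond and had started rescue by Week 48, an upper bound on responders still on rescue at that visit. By SAP 3.10, subjects enter PA0009 after at least 36 weeks on a constant dose of 160mg or 320mg, so some may have responded before any rescue. The gap does not measure what rescue caused.

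**What to change.** 1. Keep the planned analysis as the main one.
2. Add one sensitivity summary of ACR20/50/70 and PASI75/90 at Week 48, in which a subject whose first eCRF-flagged concomitant rescue medication in PA0009 started on or before that visit counts as a nonresponder.
3. Do not add prohibited medication as a trigger. Protocol Table 7-1 prohibits ad hoc analgesics in the 24 hours before a visit, so a single dose could make a subject a nonresponder from then on. It would also reverse the stated choice in SAP 13.1.2.
4. For SAP 3.10, either restore the by-subpopulation summaries of all secondary efficacy variables, including MASES and LDI, or declare their removal there and give the reason.

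Cost: one derivation and one extra table from the rescue flag and start dates already collected (SAP 6.5), plus one entry in SAP 3.10 if the summaries are not restored. The sensitivity rates cannot exceed the main ones and will be lower if any rescued subject responds. The text should say that the gap is not the effect of rescue.
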